## **8. PROGRESS REPORT**

To date a total of 47 participants have been enrolled into the study. We have successfully completed a total of 46 [C]DASB (in 18 CW, 11 REC AN, 10 REC AN-BN, 7 REC BN) and a total 47 [C]raclopride scans (in 19 CW, 11 REC AN, 10 REC AN-BN, 7 REC BN).

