## Neuroimage Analysis

MRI-Based Region of Interest (ROI) Definition for analysis of PET Data. PET and MRI image sets are aligned using PET/MRI fusion software (IDL, ITT Visual Information Solutions). ROIs are defined on MRI images across all MRI slices passing through those structures using an ROI drawing tool (imagetool) by trained tracers (blind to the diagnosis) with established reliability. For the [C]raclopride and [C]DASB studies ROIs will include the three functional sub-divisions (limbic, associative and motor) of the striatum as outlined by Martinez *et al.*. The limbic striatum comprises the AVS; the associative striatum comprises the pre-commissural DC, precommissural dorsal putamen and postcommissural DC; the motor striatum comprises the post commissural dorsal putamen. For the [C]DASB studies, as outlined by Frankle *et al.*, The subcortical regions include thalamus, insula, midbrain, medial temporal lobe (a spatially weighted average of 5 limbic structures, the uncus, amygdala, entorhinal cortex, parahippocampal gyrus, and hippocampus). The neocortical ROIs are as follows: DLPFC, medial PFC, OFC, ACC, temporal and occipital cortex. The cerebellum will be used as reference region for both studies. A different set of ROIs are routinely utilized for fMRI studies. As a result, we will define a second ROI set that will be applied to the PET BPND maps and enable us to perform the integrative analyses to relate the PET and fMRI data in exploratory AIM 4.

Anatomically constrained functional regions of interest for fMRI analyses. One of our co-investigators, [name], in collaboration with his colleagues, has developed methods for reconstructing the cortical sheet based upon routine 3D T1-weighted MRI volumes. FreeSurfer not only allows for the accurate measurement of cortical thickness, it also provides a method for parcellation of the cortical surface, where each location on the surface is assigned a neuroanatomical label based upon probabilistic information estimated from a manually labeled training set. The ROIs that will also be used for fMRI analysis include: bilateral caudate, ventral striatum, medial PFC, ACC, DLPFC, medial OFC, inferior frontal gyrus, inferior parietal cortex, and AI.

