#### Power and Statistical Analysis Plan:

**Aim 1:** In AIM 1 we will use PET and [C]DASB BPND to determine whether there is a continuum of 5-HTT binding associated with diagnosis. We hypothesize that REC AN will show increased and REC BN decreased [C]DASB BPND in midbrain and striatal regions. REC AN-BN will have [C]DASB BPNDs between those of REC AN and REC BN and will probably not differ from CW. These hypotheses will be tested by an unpaired t-test with diagnosis as factor and [C]DASB BPND as dependent variable. We will use Troendle's (1995) method to adjust for multiple comparisons. Our preliminary study found [C]McN5652 BPNDs of 1.169 (CW), 1.316 (AN), 1.027 (BN), and 1.168 (AN-BN) in the dorsal raphe, with a SD of 0.348 or less in each group. [C]McN5652 is an older radioligand and, based on additional pilot data, we expect to see [C]DASB BPNDs that are roughly 2.17-times higher than [C]McN5652 BPNDs in the midbrain, with only a

slight increase in within-group SDs (less than 0.382 for [C]DASB BPND). With 25 subjects per group, a (Welch-Satterthwaite) t-test will have power in excess of 80% to see a difference between the REC AN and CW (based on a mean difference of 0.319 and a within-group SD of 0.382) and REC BN and CW (based on a mean difference of 0.308 and a within-group SD of 0.382) at the 0.05 level (two-sided). We expect the [C]DASB BPND for REC AN-BN to be between that of REC AN and REC BN and (essentially) the same as CW.

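### Aim 1 power is stated for single t-tests at unadjusted 0.05, but the planned tests are multiplicity-adjusted over a family the plan does not define

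*Combined protocol and SAP*

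**What the plan says.** Section 9, Power and Statistical Analysis Plan, Aim 1, predicts raised [11C]DASB binding in REC AN and lowered binding in REC BN "in midbrain and striatal regions". It places REC AN-BN between the two and probably no different from CW. These hypotheses are to be tested by unpaired t-tests using Troendle's (1995) "method to adjust for multiple comparisons".

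The power statement follows: "With 25 subjects per group, a (Welch-Satterthwaite) t-test will have power in excess of 80" per cent. It covers two contrasts:
- "REC AN and CW (based on a mean difference of 0.319 and a within-group SD of 0.382")
- "REC BN and CW (based on a mean difference of 0.308 and a within-group SD of 0.382) at the 0.05 level (two-sided")

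Both differences are midbrain values, scaled from dorsal raphe results with an older ligand. The SD is given as a bound: a "slight increase in within-group SDs (less than 0.382 for" the new ligand).

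The Neuroimage Analysis section says that for both ligands "ROIs will include the three functional sub-divisions (limbic, associative and motor) of the striatum". For [11C]DASB it then adds the midbrain and a list of other subcortical and neocortical regions. Neither section says which contrasts or regions enter the Troendle adjustment, and no power figure allows for it.

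**The concern.** The power quoted is for a single test at 0.05. The planned test is one member of an adjusted family, so its critical value is at least as large and its power no higher. How much is lost depends on the size of the family, which the plan leaves open in two ways:

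- **Contrasts:** two (AN and BN vs CW), or three if AN-BN vs CW is included. The wording about testing these hypotheses comes directly after the AN-BN prediction.
- **Regions:** midbrain only, midbrain plus one striatal region, or midbrain plus the three striatal sub-divisions.

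Readers will take 80% as the chance of confirming each main prediction of the first aim, and will judge a null result against it. An open family can also be settled after the data are seen, which would undo the error control that the adjustment is meant to provide.

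**Working it through.** **Inputs from the Aim 1 paragraph.** n = 25 per group; SD 0.382; two-sided 0.05. The differences follow from the pilot means multiplied by 2.17:
- AN vs CW: 2.17 × (1.316 − 1.169) = 0.319
- BN vs CW: 2.17 × (1.169 − 1.027) = 0.308

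**Step 1: reproduce the stated figure.** Two-sample t, df = 48, d = difference / SD, noncentrality = d × √(25/2), critical value 2.011.
- AN: d = 0.319 / 0.382 = 0.835; noncentrality 2.952; power 82.5%.
- BN: d = 0.308 / 0.382 = 0.806; noncentrality 2.851; power 79.8%.

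BN falls short of 80% only at rounding level: it reaches 80% at SD 0.381, and the normal approximation gives 84.0% and 81.3%. The plan's claim therefore reproduces, but only at unadjusted 0.05.

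**Step 2: power after adjustment.** A step-down max-T procedure on Welch t statistics stands in for Troendle's stepwise resampling method. Critical values for each subset of hypotheses were taken from simulated null data. The family is varied because the plan names none. Two further inputs are assumptions: inter-region correlation 0.5 to 0.8, and a striatal effect either equal to the midbrain effect or absent. Entries are power for the midbrain contrast, AN / BN, in per cent. Monte Carlo standard error is at most 0.5 percentage points.

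| Family | SD 0.382 | SD 0.348 (assumed, favourable) |
|---|---|---|
| 2 contrasts, midbrain | 82 / 79 | 89 / 86 |
| 3 contrasts, midbrain | 74 / 71 | 82 / 79 |
| 2 contrasts × 2 regions | 69-78 / 66-75 | 78-86 / 75-84 |
| 2 contrasts × 4 regions | 57-72 / 54-69 | 69-82 / 65-79 |
| 3 contrasts × 2 regions | 62-68 / 58-64 | 72-78 / 68-75 |
| 3 contrasts × 4 regions | 52-60 / 48-57 | 63-72 / 59-69 |

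The 0.348 column uses the plan's SD bound for the older ligand. Unadjusted power at that SD is 88.8% for AN and 86.6% for BN. Separate simulations of the same procedure agree to about 1-2 points.

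**Step 3: power to confirm both predictions.** At SD 0.382 the chance that the AN and BN midbrain contrasts are both significant is about 63% in the two-test family and 19-30% with 3 contrasts × 4 regions.

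**Step 4: larger families.** The table is not a floor. All six pairwise contrasts in four regions (24 tests), with assumed correlation 0.3 or 0.7, give about 43-53% for AN and 39-49% for BN at SD 0.382.

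**The case against.** The stated figure contains no arithmetic error: the plan labels the test and the alpha level, and the number reproduces. For exactly the two contrasts it powers, a stepwise adjustment costs about one point. That narrow family is a fair reading, since AN-BN is expected to match CW and is given no power figure.

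The lower figures also depend on choices outside the documents. The 48% end assumes no striatal effect, although the plan predicts one; with equal striatal effects the same family gives 56-60% for AN and 53-57% for BN. The SD of 0.382 is an upper bound. At 0.348, several two-contrast scenarios with striatal effects reach or come close to 80%. Max-T is only a stand-in for the cited method.

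All of this is correct, and it limits how far any single adjusted figure can be relied on. It does not remove the mismatch. The hypothesis names striatal regions as well as midbrain and makes a statement about all three ED groups, so the harmless family is not the one the text most naturally suggests. With three contrasts in two or four regions, both contrasts stay below 80% even at SD 0.348. The plan also expects the SD to rise slightly with the new ligand, so 0.348 is optimistic. Nothing in the documents suggests an intention to choose the family after the fact; the point is only that nothing rules it out.

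**Conclusion.** The concern holds. The power stated for Aim 1 is correct for one unadjusted test, but it is not the power of the planned adjusted analysis, which cannot be stated until the family is named. At the plan's SD of 0.382, adjusted power per contrast runs from about 82 / 79% (two midbrain contrasts) down to 52-60 / 48-57% (three contrasts, four regions). Every family examined that is larger than two midbrain contrasts leaves both contrasts below 80%. The mismatch and the missing family can be read directly from the text. The size of the loss depends on the assumed family, correlation, striatal effect and SD. This should be corrected, but it does not invalidate the study.

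**What to change.** State in the Aim 1 paragraph which group contrasts and which regions form the family for Troendle's adjustment, and label all other regions exploratory. Replace the power sentence with power for the adjusted tests, showing the assumed SD, striatal effects and inter-region correlation.

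Two of these inputs can come from the study itself. The Progress Report says: "We have successfully completed a total of 46" [11C]DASB scans. Residuals after centring each group give a pooled within-group SD on 46 − 4 = 42 degrees of freedom, together with the midbrain-striatum correlation. Group means need not be reported or compared, so the family can be fixed without looking at the contrasts of interest.

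Optionally, add the AN vs BN comparison as supporting evidence only. The plan's inputs imply a difference of 0.319 + 0.308 = 0.627, d = 0.627 / 0.382 = 1.64, with power above 0.99 even at 0.05/12.

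The cost is SAP wording and one recalculation, with no change to design or sample size. The downside is that the stated power against CW will probably look less favourable, and a narrow family leaves the remaining regions without confirmatory status.

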#### Exploration of group differences for endogenous DA release in striatal regions of interest (ROIs)

**Limbic striatal:** Some, but not all, data show that mixed groups of REC AN and AN-BN have elevated baseline AVS [C]raclopride BPND compared to CW. While pilot data in a mixed group of REC AN and AN-BN showed a non-significant reduction of endogenous DA release in the AVS, an earlier study from our group showed that only the REC AN (pure restricting-type) had significant reduction of the DA metabolite HVA in CSF compared to CW. In Parkinson’s disease there is diminished CSF HVA and extracellular DA. We seek to determine whether pure REC AN (never had BN) have reduced endogenous DA AVS release when compared to CW. Because endogenous DA displaces raclopride at the D2 receptor, elevated DA D2 receptor binding is consistent with diminished DA release. Altered AVS DA function in “pure” restricting-type AN group is likely given that this subtype has substantial anhedonia and reduced consummatory drive and other evidence of dysregulated AVS function.

With regards to predictions of AMPH induced DA release in REC BN and AN-BN, there are limited background data. The pilot data from our group showed a non-significant baseline [C]raclopride BPND increase in the AVS in REC BN, but a very large standard deviation (SD). Moreover, REC BN and AN-BN have normal CSF HVA levels, and ill BN have normal limbic DA release. Together these data suggest that we will find normal limbic striatal DA release in REC BN. However, most studies to date have investigated mixed groups of AN and AN-BN, or BN and AN-BN. One advantage of the current study is that we are recruiting substantial numbers of “pure” subtypes. For example, the AN have never had BN symptoms. Second, data about DA release are critical for understanding DA’s relationship to anxiety and inhibition (AIM 2C) and to building a model (see below) regarding limbic and associative DA balance for the 3 subgroups.

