**Aim 2A** will compare REC AN, REC AN-BN and REC BN to CW to test the hypothesis that REC AN and REC BN have increased AVS [C]raclopride BPND compared to CW, and to further explore [C]raclopride BPND in REC AN-BN. We will assess [C]raclopride BPND in ventral and dorsal putamen, ventral and DC and consider the influences of age, weight, and other relevant variables. These hypotheses will be tested by an unpaired t-test, with diagnosis as factor and [C]raclopride BPND as dependent variable. We will use Troendle's (1995) method to adjust for multiple comparisons. Based on our pilot data we expect to see [C]raclopride BPND of roughly 2.120 (CW), 2.404 (REC AN), 2.299 (REC BN), and 2.147 (REC AN-BN) in the AVS, with SDs of roughly 0.359 in each group. With 25 subjects per group, a (Welch-Satterthwaite) t-test will have power in excess of 90% to detect differences in [C]raclopride BPND between each of the ED groups and CW at the 0.05 level (two-sided). We will also regress log [C]raclopride BPND on group (REC AN, REC AN-BN, and REC BN, with CW as the reference group), controlling for age, height, and weight. To the extent that these additional covariates are associated with log [C]raclopride BPND, this will reduce the standard error associated with each of the group effects leading to improved power.

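### Aim 2A plans on an AVS SD of about 0.359 for every group, but the Background reports a very large REC BN pilot SD: the REC BN input is unsupported, and the four-group regression states no variance structure

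*Combined protocol and SAP*

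**What the plan says.** All planning text is in section 9, Power and Statistical Analysis Plan, Aim 2A, unless noted.

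- **Means and SD.** Expected AVS binding is "2.120 (CW), 2.404 (REC AN), 2.299 (REC BN), and 2.147 (REC AN-BN) in the AVS". The SD is the same for all four groups: "in the AVS, with SDs of roughly 0.359 in each group". The source is described only as the team's pilot data, without a citation.
- **Power.** "With 25 subjects per group, a (Welch-Satterthwaite) t-test will have power in excess of 90% to detect differences in" binding "between each of the ED groups and CW at the 0.05 level (two-sided").
- **Hypothesis test.** "These hypotheses will be tested by an unpaired t-test, with diagnosis as factor and" binding as the outcome. The stated hypotheses are for REC AN and REC BN against CW; REC AN-BN is exploratory. Multiplicity: "We will use Troendle's (1995) method to adjust for multiple comparisons".
- **Additional regression.** Log binding is regressed on group (CW as reference), age, height and weight. The plan adds that, so far as the covariates are associated with the outcome, "this will reduce the standard error associated with each of the group effects leading to improved power". It states no error structure and no standard-error method.
- **Section 7, Background, limbic striatal paragraphs.** The team's pilot of baseline AVS raclopride binding showed a non-significant increase in REC BN, "but a very large standard deviation (SD"). The remark is made about REC BN only, and no value is given.

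**The concern.** The two sections describe the same measure, region and group, and both appeal to the team's pilot data. One singles out REC BN as highly variable; the other gives REC BN the same SD as everyone else. If REC BN is the more variable group, two things follow.

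First, REC BN vs CW, one of the two hypothesised Aim 2A contrasts, has less power than an SD of 0.359 implies. This is separate from whether the printed power follows from 0.359: correcting that arithmetic alone would leave a REC BN figure resting on an SD that the protocol itself calls into question.

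Second, the power statement uses a Welch test, which allows unequal variances, while the regression that follows says nothing about them. The ordinary reading is least squares with one residual variance shared by four groups. That would carry excess REC BN variance into the REC AN contrast and understate the standard error of the REC BN contrast.

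**Working it through.** **Inputs.** n = 25 per group, two-sided alpha 0.05, SD 0.359. Differences from CW: REC AN 2.404 − 2.120 = 0.284; REC BN 2.299 − 2.120 = 0.179; REC AN-BN 2.147 − 2.120 = 0.027. All are from the Aim 2A paragraph. The REC BN SD is an assumption, written as k times the SD of the other groups, with k = 1, 1.25, 1.5 and 2.

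**Step 1: the plan's own figure.** SE = √(0.359²/25 + 0.359²/25) = 0.1015, with 48 degrees of freedom and critical t 2.011. The noncentrality is the difference divided by the SE.

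| Contrast with CW | Noncentrality | Power |
|---|---|---|
| REC AN | 0.284/0.1015 = 2.80 | 78% |
| REC BN | 0.179/0.1015 = 1.76 | 41% |
| REC AN-BN | 0.027/0.1015 = 0.27 | 6% |

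The printed figure of more than 90% for each contrast is not reproduced. One-sided testing gives 87%, 54% and 8%; 30 per group two-sided gives 85%, 48% and 6%.

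**Step 2: REC BN vs CW with a larger REC BN SD (Welch, noncentral t).** Two readings of 0.359 are possible.

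*Reading A:* 0.359 is the SD of CW, REC AN and REC AN-BN, and REC BN has k × 0.359. At k = 1.5, SE = √(0.359²/25 + 0.5385²/25) = 0.129, noncentrality 1.38 and about 42 degrees of freedom, giving 27%.

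*Reading B:* 0.359 is a pooled SD that already includes REC BN. The other groups then have s = 0.359/√((3 + k²)/4) and REC BN has ks. At k = 1.5, s = 0.359/√1.3125 = 0.313 and the REC BN SD is 0.470.

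| k | Power, reading A | Power, reading B |
|---|---|---|
| 1 | 41% | 41% |
| 1.25 | 33% | 37% |
| 1.5 | 27% | 34% |
| 2 | 19% | 30% |

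**Step 3: REC AN vs CW by Welch.** The test uses only the REC AN and CW variances. Power stays at 78% for every k under reading A. Under reading B it rises (83%, 88% and 95% at k = 1.25, 1.5 and 2), because s is then below 0.359.

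**Step 4: the regression with one residual variance.** With equal groups the pooled variance is s²(3 + k²)/4.

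- For REC AN vs CW the correct variance uses s², so the SE is too large by √((3 + k²)/4): 1.07, 1.15 and 1.32 at k = 1.25, 1.5 and 2.
- For REC BN vs CW the correct average variance is s²(1 + k²)/2. At k = 1.5 this is 1.625s² against a pooled 1.3125s², so the SE is too small.

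Simulated rejection rates on the raw scale, without covariates, normal data:

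| k | REC BN vs CW, null | REC AN vs CW, null | REC AN power, A | REC AN power, B |
|---|---|---|---|---|
| 1 | 5% | 5% | 79% | 79% |
| 1.25 | 6% | 3.5% | 75% | 81% |
| 1.5 | 8% | 2.5% | 70% | 82% |
| 2 | 10% | 1% | 57% | 86% |

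The null rates are the same under both readings, since they depend only on k. For every k above 1, REC AN power is below the Welch value in step 3. The same model on log-transformed values, under reading A, gives REC BN null rejection of about 7%, 9% and 16% and REC AN power of 73%, 67% and 48% at k = 1.25, 1.5 and 2.

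**The case against.** The strongest reply is that no conflict is proven. No REC BN SD is printed, and a very large SD is a description, not a number. It follows directly on a non-significant increase, and an SD of 0.359 is already twice the expected REC BN difference of 0.179, so an author might describe 0.359 itself in those words. The Aim 2A paragraph does not name its pilot data set, so identity with the one in the Background is inferred. This stands. A reader might infer that 0.359 is wrong for REC BN; the documents do not show that.

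A reader might also infer that unequal variance distorts the REC AN comparison in general. It does not. The hypotheses are tested by t-test, the power statement names the Welch form, and that test ignores the REC BN variance. The regression is an addition, on the log scale, where the variance ratio is unknown, and its single residual variance is only the usual reading of an unspecified model. Nor does its REC AN power necessarily fall below plan: under reading B it is 79% to 86%.

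Finally, the improved-power sentence is conditional and concerns adding covariates. It makes no comparison with Welch and need not be called false.

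What does not fall away: the remark is specific to REC BN, the two sections are not reconciled, and the false-positive inflation for REC BN in a one-variance model is the same under either reading.

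**Conclusion.** The point holds in limited form. The REC BN planning SD is unsupported and unreconciled with the Background. On the printed inputs, Welch power for REC BN vs CW is about 41%, and it is lower under both readings if REC BN is the more variable group: 19% to 33% if 0.359 describes the other groups, 30% to 37% if it is pooled, for assumed ratios of 1.25 to 2. Most of the gap from the stated 90% comes from the arithmetic on 0.359; the variance question accounts for the rest.

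The Welch test of REC AN vs CW is not affected. The supplementary regression is at risk only if it is fitted with one residual variance and REC BN is in fact more variable. It would then be anti-conservative for REC BN vs CW (about 6%, 8% and 10% at ratios 1.25, 1.5 and 2, as a raw-scale illustration), and conservative and less powerful than Welch for REC AN vs CW.

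**What to change.** 1. In the Aim 2A power paragraph, give each group's pilot AVS SD and name the data set it comes from. Reconcile the REC BN value with the Background remark, or explain why that pilot was set aside. Restate power separately for each contrast with those SDs.
2. Specify that the Aim 2A regression of log binding on group, age, height and weight uses HC3 standard errors or group-specific residual variances, in line with the Welch test already chosen.

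The cost is wording and one software option, with no new data or participants. The stated REC BN power becomes less favourable. If the variances prove equal, about one point of power is lost for REC AN vs CW (78% against 79%).

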**Aim 2C** Relationships between [C]raclopride  $\Delta$  BPND and behavioral characteristics (from assessments and VAS scales) and plasma AMPH levels of subjects will be analyzed with Pearson Product-Moment correlation coefficient. For example, we will compare the Fisher's z-transformed correlations between behavioral measures of euphoria and anxiety with [C]raclopride  $\Delta$  BPND in REC AN, REC AN-BN and REC BN vs. CW using a t-test. Based on our pilot data in REC AN, we expect correlations between euphoria and [C]raclopride  $\Delta$  BPND in the AVS to be larger (in magnitude) than -0.69 in CW and 0.21 in REC AN subjects. Assuming a difference in Fisher's z-transformed correlations of 1.06 (or larger), we will have power 0.91 to see a group difference at the 0.05 level (two-sided), with 20 subjects per group. (Note that the z-transformed value of 0.69 is -0.85, and the z-transformed value of 0.21 is 0.21, giving a difference of 0.21 - (-0.85) = 1.06). Similarly, we will correlate DA release with self-ratings of anxiety, euphoria, self-control, and labile mood in striatal regions in order to assess behavioral response, as well as SSRT and post-study food consumption. We will use continuous

measures of impulse control and inhibition including the SSS, BIS-11, EDI-2-subscale impulse regulation, novelty seeking and HA from the TCI and the basic stop signal task. It is not certain what to expect from the REC BN and REC AN-BN subjects, but we will look for differences in correlations in the same way. Assuming these differences are larger than 0.909, we will have power in excess of 0.80 to see group differences at the 0.05 level (two-sided). We will explore the effects of age, height, and weight on DA release using partial correlations, after controlling for these variables.

Spontaneous Eye Blink Rate: Collecting of eye blink rate data will be done two times during the study, shortly before the 1st [C]raclopride scan (baseline), and shortly before the 2nd [C]raclopride (post-AMPH) scan. Spontaneous eye blink rate will be measured by having participants sit in front of a computer screen that is equipped with a video recording device. Participants will be told to look at the fixation cross in the center of the screen for a duration of five minutes with the explanation that we are interested in recording aspects of facial movements. Participants will not be told that blink rates are the object of the fixation to ensure that blink rates truly are spontaneous and are not being intentionally manipulated by the participant. Data will subsequently be scored by averaging across each five minute span to obtain a blink per minute rate, similar to prior work using this methodology.

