## 10. HUMAN SUBJECTS

Subject Population: We seek to recruit 30 REC AN, 30 REC AN-BN, 30 REC BN, and 30 CW, between ages 18 to 45 for the PET imaging studies. It is our experience from previous studies that it will be necessary to enroll an additional 20% of subjects due to drug failure, non-completion of PET studies, etc. Thus, we expect to complete PET studies in a total of 100 subjects (25 REC AN, 25 REC AN-BN, 25 REC BN, and 25 CW).

Only right-handed subjects will be included as screened by the Edinburgh Handedness Inventory. The rationale for including only female subjects is that AN, AN-BN and BN among males is relatively rare (less than 10% in our experience). Furthermore, because some males with AN, AN-BN or BN have many atypical features, they should be subjects of a different study. All subjects will be matched by age, IQ, income, race/ethnicity, and will be non-smokers. REC AN, REC AN-BN, REC BN, and CW will be matched by BMI. Subjects will be recruited locally and nationally to reflect the racial/ethnic composition of the United States, which encompasses a wide range of ethnically diverse individuals (i.e., 65.6% White persons, not Hispanic, 15.4% Hispanic or Latino origin, 0.2% Native Hawaiian and Other Pacific Islander, 4.5% Asian persons, 1.0% American Indian and Alaska Native persons, 12.8% Black persons, 79.8% White persons (<http://quickfacts.census.gov/qfd/states/00000.html>)). While every effort will be made to recruit participants in respective proportion to these demographics, it has been our experience that patients with AN, AN-BN and BN tend to be predominantly white. Subjects fulfilling all the inclusion, but none of the exclusion criteria, will be admitted to the study. No exclusion criteria shall be based on race or ethnicity.

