## 11. RECRUITMENT

This is a five-year study in which we will recruit equal numbers of subjects each year. It is our experience from previous studies that it will be necessary to enroll an additional 20% of subjects due to drug failure, non-completion of PET studies, etc. Thus, we expect to enter 30 subjects to complete cells of 25 radioligand/PET studies per subject group. Overall, we will enter 120 subjects into this study in 5 years or 24 subjects per year.

Since at least 50 to 70% of individuals who have anorexia or bulimia eventually recover, we are confident that our recruitment goal can be achieved over the proposed 5-year period. All CW will be recruited from the greater San Diego region to minimize travel cost. However, based on our experience, approximately 75% of our REC subjects will come from outside southern California.

We will continue to employ recruitment strategies that were effective in our previous studies. These include: a) mailings to former patients of UCSD and the University of Pittsburgh ED treatment programs and other nationally recognized ED treatment programs directed by colleagues; b) mailings of IRB approved flyers to clinicians and treatment centers specialized in EDs, and to university health and counseling centers; c) placing advertisements and study announcements in ED related publications, press releases and conferences (e.g., NEDA, AED and EDRS); d) placing study advertisements on websites such as EDReferral and NEDA. We will also utilize the UCSD research websites which make available to professionals and the lay public alike our research publications and current findings; e) We may also contact participants who have been in our previous studies and who appear to be appropriate potential participants for this current study, provided they have given written permission to recontact them. There will be no cold-calling to any potential participant.

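### Aim 2C: a t-test does not fit one Fisher z per group; power at 20 per group is 0.87 to 0.89, not the stated 0.91, and the second power claim gives no n

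*Combined protocol and SAP*

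**What the plan says.** In section 9, Power and Statistical Analysis Plan, Aim 2C correlates the amphetamine-induced change in raclopride binding with behavioural ratings. It then compares the Fisher z-transformed correlations "in REC AN, REC AN-BN and REC BN vs. CW using a t-test".

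The worked example concerns euphoria and the anterior ventral striatum. The assumed correlations are -0.69 in controls and 0.21 in REC AN, which the plan converts to a difference in "z-transformed correlations of 1.06 (or larger"). For that difference it states: "we will have power 0.91 to see a group difference at the 0.05 level (two-sided), with 20 subjects per group".

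For REC BN and REC AN-BN the plan says it is unsure what to expect and will look for differences by the same approach. It adds: "Assuming these differences are larger than 0.909, we will have power in excess of 0.80 to see group differences", again at two-sided 0.05. That sentence gives no sample size.

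Elsewhere the planned number of completers is 25 per group. Section 10 says "we expect to complete PET studies in a total of 100 subjects", split equally over four groups, and section 11 says "we expect to enter 30 subjects to complete cells of 25 radioligand/PET studies per subject group". The power text for Aims 1 and 2A uses 25 per group; that for Aim 2B uses 20.

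**The concern.** A two-sample t-test needs replicate observations in each group to estimate a variance. Here each group contributes a single correlation, hence a single z. The sampling variance of z is known approximately from theory, 1/(n-3), so the difference between two groups is referred to the standard normal distribution. Taken literally, the named test cannot be carried out on the quantities compared.

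The power figure has a related fault. It is the only Aim 2C power printed with an n, and it should follow from its own inputs. If it does not, the reader is given a power that the stated design does not deliver. The second sentence cannot be checked as printed, and whether its claim is true depends on which of the plan's two sample sizes applies.

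**Working it through.** **Inputs, all from Aim 2C unless noted**

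- Correlations: -0.69 (controls) and 0.21 (REC AN)
- n = 20 per group for the first power statement
- Two-sided alpha 0.05
- Second difference: 0.909, no n given
- Planned completers: 25 per group (sections 10 and 11)

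**Step 1. The plan's effect size.** atanh(0.69) = 0.848 and atanh(0.21) = 0.213. The difference is 0.848 + 0.213 = 1.061, so the plan's 1.06 reproduces.

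**Step 2. Where the plan's power figures may come from.** Suppose the z difference is treated as a difference in means with a per-subject SD of 1. At n = 20 this gives SE = sqrt(2/20) = 0.316 with 38 degrees of freedom. Power for 1.06 is then 0.904, and the 80% detectable difference is 0.909. The second value matches the plan to three decimals and the first comes close to 0.91. However, the Fisher formula at n = 22, SE = sqrt(2/19) = 0.324, gives the same pair (0.904 and 0.909). The origin is therefore an inference: either an SE that is not valid for correlations, or an n that is not printed.

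**Step 3. Power with the Fisher z test.**

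SE = sqrt(1/(n1-3) + 1/(n2-3)); power = Φ(d/SE - 1.960) + Φ(-d/SE - 1.960). The second term is negligible here.

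At n = 20, SE = sqrt(2/17) = 0.3430:

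- d = 1.06: 1.06/0.3430 = 3.09; 3.09 - 1.96 = 1.13; power 0.871
- d = 0.909: 0.909/0.3430 = 2.65; 2.65 - 1.96 = 0.69; power 0.755
- Difference needed for power 0.91: 0.3430 × (1.960 + 1.341) = 1.132
- 80% detectable difference: 0.3430 × (1.960 + 0.842) = 0.961

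At n = 25, SE = sqrt(2/22) = 0.3015:

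- d = 1.06: power 0.940
- d = 0.909: power 0.854
- 80% detectable difference: 0.3015 × 2.802 = 0.845

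**Step 4. Simulation.** The formula is an approximation, so the same test was run on simulated bivariate normal data (400,000 replicates, Monte Carlo SE below 0.001).

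| Difference | n per group | Plan states | Formula | Simulation |
|---|---|---|---|---|
| 1.06 (-0.69 vs 0.21) | 20 | 0.91 | 0.871 | 0.888 |
| 1.06 | 22 | – | 0.904 | 0.918 |
| 1.06 | 23 | – | 0.918 | – |
| 1.06 | 25 | – | 0.940 | 0.949 |
| 0.909 | 20 | >0.80, n not stated | 0.755 | 0.777–0.779 |
| 0.909 | 25 | >0.80, n not stated | 0.854 | 0.869–0.870 |

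The two simulated values for 0.909 come from fixing one correlation at -0.69 and from placing the pair symmetrically about zero. The type I error of the test at n = 20 was 0.049 to 0.050, so the test itself behaves properly. Power 0.91 for a difference of 1.06 is first reached at 23 per group by formula and 22 by simulation.

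**The case against.** The strongest reply has four parts.

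*The n behind the second sentence can be inferred.* The text names a t-test and 20 per group and says the other groups are handled alike. A t-test with SD 1 at n = 20 gives exactly 0.909 as the 80% detectable difference; at n = 25 the same calculation gives 0.809. This is a reasonable inference, but the Fisher formula at n = 22 gives 0.909 too, so it is not settled. If 20 is right, the claim of more than 0.80 fails under the correct SE.

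*The gap is small.* Simulation is the better guide and puts the shortfall near 2 points. This stands and limits the weight of the point. It does not make 0.91 correct.

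*The effects are stated as lower bounds.* They are, but a power quoted for a minimum effect must be reached at that minimum. By formula, 0.91 at 20 per group needs a difference of about 1.13.

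*Nothing follows for the study.* With 25 completers per group both statements hold, and even at 20 the REC AN comparison keeps power above 0.80. This also stands. What remains is a test that does not fit its data, one incorrect figure, and one claim that cannot be checked.

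**Conclusion.** The concern holds and is minor. The named t-test does not fit a comparison of one Fisher z per group. At the stated 20 per group, power for a difference of 1.06 is 0.871 by formula and 0.888 by simulation, against a printed 0.91. The claim of more than 0.80 for differences above 0.909 is false at 20 per group and true at 25, and the sentence does not say which applies.

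These results assume bivariate normal data, equal group sizes, independent groups, two-sided 0.05 without multiplicity adjustment as in the plan's own calculation, and the plan's assumed correlations. They do not show the study to be underpowered: at 25 usable paired scans per group, the formula gives 0.940 and 0.854.

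**What to change.** In Aim 2C, replace the t-test with the two-sample Fisher z test, SE = sqrt(1/(n1-3)+1/(n2-3)), referred to the standard normal distribution. State one n per group for both power sentences and print the powers that belong to it:

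- If n = 20: about 0.87 for a difference of 1.06 and 0.76 for 0.909, with 0.96 as the 80% detectable difference.
- If 25 paired baseline and post-amphetamine scans per group are expected: about 0.94 and 0.85.

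These are formula values. If simulated values are preferred (0.89 and 0.78 at 20; 0.95 and 0.87 at 25), say so.

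For the exploratory partial correlations, add only that the number of covariates is also subtracted from each n in the SE. Print no power for them, because the plan does not give the adjusted correlations.

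The cost is the wording of the test, one stated n and two power figures. Data collection, sample size and hypotheses do not change.
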